While estimates of effectiveness success after catheter ablation also vary widely, primarily due to length of follow-up, severity of AF, and the definition of failure utilized, the overall success in a persistent population at 12 months, as defined by current guidelines, is believed to be less than 60%. In particular, the only regulatory trial for catheter ablation of atrial fibrillation with posted trial results, the Medtronic Ablation Frontiers TTOP trial, which utilized a similar population with a less stringent endpoint of a 90% reduction in AF after only 6 months of follow-up 3 months beyond the blanking period), had a success rate of 55.8%^{30, 31, 32}. A recent study in Spain (SARA) reported that 60.2% (59 of 98) of persistent AF patients (where LS persistent patients were excluded) were free of any recurrence of >30 s at 12 months follow-up³³. A report of 5-year outcomes in a LS persistent AF population of 202 patients showed that 35% remained in SR at 1 year after a single catheter ablation and 58% remained in SR at 1 year after multiple procedures, with persistent AF duration a highly significant predictor of relapse³⁴.

Based on a thorough review of the literature, an OPC of 60% success was chosen as the acceptable lower confidence limit for effectiveness in the combined persistent and LS persistent populations of this study. Thus, the goal for the primary effectiveness endpoint is to establish that the DEEP procedure significantly increases effectiveness relative to an OPC of a 60% catheter ablation success rate. Using the expected effectiveness success rate of 70% for the DEEP procedure, a one-sided alpha=0.025 level of significance, and a normal approximation to the binomial distribution with continuity correction, a sample size of N=182 is required to ensure 80% power.

Safety

Due to the groundbreaking new procedure that will be utilized in this trial, there are no regulatory trials with reported safety results for any type of similar minimally invasive procedure. The published literature for similar procedures is sparse and safety events are not reported with any consistency. Thus, the only realistic estimate of safety event rates is derived from the most recent feasibility trial. Based on this trial, a best estimate of the primary safety event rate over the dual procedures is 19%.

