The primary effectiveness and safety endpoints require similar numbers of patients, with the effectiveness endpoint driving the overall sample size. Due to the potential for significant loss to follow-up prior to the primary effectiveness endpoint at 12 months. In order to allow for an attrition rate of approximately 20%, this study will treat up to 220 subjects.

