where p_E = the proportion of primary effectiveness successes. The ITT population will be the primary population for this analysis and the LOCF method will be the primary missing value method, as described in the Missing Values section below.

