2.1.1 Primary Effectiveness Endpoint

The primary effectiveness endpoint is freedom from any documented AF, atrial flutter, or atrial tachycardia lasting >30 seconds in duration through the 12-month follow-up visit in the absence of Class I or III AADs (with the exception of previously failed AADs at doses not exceeding those previously failed).

Any arrhythmia that occurs within the blanking period or the AAD Optimization period will not be considered a failure (Visit 5 up to Visit 10). The rhythm status used for evaluation of this endpoint will be derived from regularly scheduled monitoring (i.e. Holter, Zio™-Patch, or 30 second ECG) as well as any symptom driven monitoring that is performed.

The following scenarios shall constitute a failure of the primary effectiveness endpoint:

1. Any documented AF, atrial flutter, or atrial tachycardia lasting >30 seconds duration that occurs at any time beginning at the 6-month visit and through the 12-month visit. These will be

Statistical Analysis Plan		Page 6 of 22
Sponsor	Study	Version
AtriCure	DEEP Pivotal Study	Version 2.0

documented on any Core Lab – ECG form with a time interval of “6 Month Post Endocardial” or “12 Month Post Endocardial”.

2. Any previously failed class I or III AAD administered at a dose higher than baseline and between the 6-month visit date plus one day and the 12-month visit date.
3. Any newly introduced class I or III AAD usage beginning at the 6-month visit date plus one day and through the 12-month visit date.
4. DC cardioversion for AF, atrial flutter, or atrial tachycardia that takes place at any time beginning at the 6-month visit date and ending at the 12-month visit date.
5. Catheter ablation or surgical treatment for AF, atrial flutter, atrial tachycardia that takes place at any time beginning at the 3-month visit date and ending at the 12-month visit date.
6. Two or more repeat catheter ablations within the 2nd blanking period.
7. The use of a non-AtriCure study device for creation of any lesions during the surgical epicardial ablation procedure.

For the purposes of this study, atrioventricular nodal reentrant tachycardia (AVNRT), inappropriate sinus tachycardia, and Wolff–Parkinson–White syndrome (WPW) will not be considered procedure failures.

For this study, AtriCure defines failure of an antiarrhythmic drug (AAD) to include ineffectiveness or intolerance of the AAD.

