5.2 Analysis Populations

Intent to treat patient population (ITT): The ITT subject population will include all subjects who have met all inclusion/exclusion criteria and on whom a procedure was attempted (defined as a subject who underwent induction of anesthesia).

Modified intent to treat patient population (mITT): The mITT subject population will include all subjects who attempted the Epicardial Procedure (defined as a subject who underwent induction of anesthesia) and have at least one post-procedure follow-up visit after the 2nd Blanking Period (with the 2nd blanking period defined as the 90-days post Endocardial Ablation Procedure) with non-missing primary effectiveness data.

Safety Population: The safety population will include all enrolled subjects that undergo induction of anesthesia.

Per protocol patient population (PP): The PP patient population will include all subjects who complete both the Epicardial Surgical Ablation Procedure and Endocardial EP Ablation Procedure.

AtriClip Effectiveness population: The AtriClip effectiveness population will include all ITT subjects for whom an attempt (entrance of the AtriClip into the chest wall) is made to place an AtriClip device.

The primary effectiveness analysis will utilize the mITT patient population as defined in this statistical analysis plan. The analysis will be repeated on the ITT and PP patient populations as supportive analyses. Secondary effectiveness analyses will be conducted on the mITT, the ITT and the PP patient populations. All safety analyses will utilize the safety population.

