5.3 Handling of Missing Data

All safety analysis will utilize the safety population and no missing values will be imputed unless a subject misses a follow-up visit and cannot subsequently be contacted to determine their primary safety status. In this case, the primary safety endpoint will be considered a failure and the subject will be excluded from any subsequent secondary safety analyses for which their status is unknown. If a procedure is aborted due to a primary safety event, the subject will be considered a safety failure. If a subject misses a follow up visit, but it can be subsequently verified that the subject did not incur a safety failure, the subject will be considered a success. As an additional analysis, the primary safety endpoint will be analyzed based on only observed failures, with all other subjects in the Safety Population counting as a success.

The primary effectiveness analysis will utilize the mITT population and the LOCF method for missing values, as defined below. A subject with any primary effectiveness failure from the 6-month visit

Statistical Analysis Plan		Page 12 of 22
Sponsor	Study	Version
AtriCure	DEEP Pivotal Study	Version 2.0

through the 12-month visit will be considered a failure for all methods below. Any subjects who withdraw or are lost-to-follow-up after the 6-months visit (post AAD optimization) but prior to the 12-month follow-up visit, or for any reason do not have 12-month ECG readings available, will be analyzed as follows:

- 1) Last observation carried forward (LOCF): Any subject who is missing a scheduled testing will be considered an effectiveness success or failure at that scheduled visit based on their status up to and including their last testing.
- 2) Worst case: Any subject with no primary effectiveness failure recorded and with no 12-month test data will be considered a failure.
- 3) Best case: Any subject with no primary effectiveness failure recorded and with no 12-month test data will be considered a success.
- 4) Break-even: If the study endpoint is met using the best-case methodology and is not met using the worst-case methodology, a break-even analysis will be performed to determine the number of subjects with missing endpoint data who would be required to be a success in order to meet the endpoint.

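### Followed literally, LOCF scores an ITT subject who dies or exits before the 6-month visit as an effectiveness success, so the ITT rate rises with early loss

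*SAP*

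**What the plan says.** **Who is in ITT.** SAP 5.2 admits every eligible subject who underwent induction of anesthesia and requires no follow-up. The SAP's primary population is mITT, which requires a visit after the second blanking period with non-missing primary effectiveness data. Of the others it says: "The analysis will be repeated on the ITT and PP patient populations as supportive analyses". Protocol 9.7.1 differs: "The ITT population will be the primary population for this analysis and the LOCF method will be the primary missing value method".

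**What can count as a failure.** SAP 2.1.1: "Any arrhythmia that occurs within the blanking period or the AAD Optimization period will not be considered a failure (Visit 5 up to Visit 10"). Protocol 3.6 also leaves recurrence in the first blanking period unevaluated. Of the seven failure items, only items 5 to 7 (ablation or surgery from the 3-month visit, two or more repeat ablations in the second blanking period, a non-study device at surgery) can arise before Visit 10. Death is not on the list.

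**How a missing 12-month result is handled.** The SAP 5.3 lead-in has two limbs: withdrawal or loss after the 6-month visit, and absence of 12-month ECG readings for any cause. Protocol 9.9 is wider and covers any loss before the 12-month visit. Under LOCF the subject "will be considered an effectiveness success or failure at that scheduled visit based on their status up to and including their last testing". Worst-case, best-case and break-even analyses follow in both documents.

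**What the default is.** SAP 5.6.1.1 and Protocol 9.7.1 call a subject a success when no failure was recorded between the 6-month and 12-month visits.

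**The concern.** A subject who leaves before Visit 10 has, at most, 30-second ECGs taken while arrhythmia could not count. Continuous and symptom-driven monitoring begin only at the 6-month visit (Protocol 7.13). The effectiveness status carried forward is that no failure was recorded, which the plan defines as success.

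Such subjects are foreseen. Protocol 4.4 lets a subject who withdraws before the endocardial stage exit after the 1-month visit, and some subjects may die or be lost.

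A supportive ITT analysis should show whether the mITT result depends on who stayed. An ITT rate that improves with each early loss cannot do that. Where ITT with LOCF is the primary analysis, as in the protocol, the error reaches the success criterion itself.

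**Working it through.** **Inputs**
- Null rate 60%: "an OPC of 60% success was chosen as the acceptable lower confidence limit for effectiveness" (Protocol 9.3).
- Expected rate 70%: "Using the expected effectiveness success rate of 70% for the DEEP procedure" (Protocol 9.3).
- Error level: "a one-sided alpha=0.025 level of significance" (Protocol 9.3).
- Number treated: "In order to allow for an attrition rate of approximately 20%, this study will treat up to 220 subjects" (Protocol 9.3).
- Share leaving before Visit 10: not stated. It is taken as an assumption, with a range shown.

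**The plan's own figure.** n = [(1.960·√(0.6·0.4) + 0.842·√(0.7·0.3)) / 0.10]² = 181.1, so 182, which is the stated N. This reproduces only without the continuity correction that Protocol 9.3 names. With it, (n/4)·[1 + √(1 + 2/(0.10·n))]² = 191.0, rounded up to 192. That is a side observation and does not affect what follows.

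**How an early leaver is scored**
1. The subject is eligible, was anesthetized and leaves before Visit 10, so is in ITT.
2. There are no 12-month ECG readings, so the second limb of the SAP 5.3 lead-in applies.
3. Any arrhythmia seen so far is not a failure (SAP 2.1.1), and death is not a failure.
4. Unless one of items 5 to 7 applies, no failure is recorded, and SAP 5.6.1.1 gives success.
5. Best case gives the same answer for this subject, and worst case the opposite.

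**Cut-off at N=220.** The smallest r with P(Bin(220, 0.6) ≥ r) ≤ 0.025 is 147 (66.8%). The protocol's exact test and the SAP's chi-squared test (uncorrected) share this cut-off. Actual size is 2.2%, and power at 70% is 86.5%.

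**Effect of k early leavers scored as successes.** The test passes when the other 220−k subjects supply at least 147−k successes:
- P(pass) = P(Bin(220−k, p) ≥ 147−k)
- Expected ITT rate under LOCF = [p·(220−k) + k] / 220
- Expected ITT rate with leavers as failures = p·(220−k) / 220

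| k | share of 220 | P(pass), p = 60% | ITT rate under LOCF, p = 70% | ITT rate, leavers as failures, p = 70% |
|---|---|---|---|---|
| 0 | 0% | 2.2% | 70.0% | 70.0% |
| 2 | 0.9% | 2.8% | 70.3% | 69.4% |
| 9 | 4.1% | 6.2% | 71.2% | 67.1% |
| 22 | 10% | 20.5% | 73.0% | 63.0% |
| 37 | 16.8% | 52.0% | 75.0% | 58.2% |

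With k = 22, the success rate needed among the remaining 198 falls from 66.8% to 125/198 = 63.1%. With p = 70% and k = 22, the chance of passing is 98% under LOCF and 11% with leavers as failures.

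**Where the k values come from.** Nine is 1/25 of 220 (8.8, rounded up): in the staged feasibility study 24 of the 25 surgically treated subjects received the endocardial procedure (Protocol 1.0). Twenty-two is 10%. Thirty-seven is nearly the whole margin of 220 − 182 = 38, with all of it placed before Visit 10.

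**The case against.** **The authors may have meant only later losses.** The first limb of the SAP 5.3 lead-in speaks of losses after the 6-month visit, and Protocol 9.9 lacks those words. LOCF could also be read as carrying forward the raw rhythm on the last ECG, which would fail a subject for blanked AF. This has weight as evidence of intent. But the second limb still catches early leavers, and the success default fits the first reading better. If the second limb is set aside, these subjects have no LOCF rule at all. An explicit sentence is needed either way.

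**The SAP's confirmatory test is not affected.** A reader might infer that the SAP's primary analysis has an inflated false-positive rate. The documents do not support that: mITT is primary there and its entry rule requires effectiveness data, while ITT is supportive and spends no alpha. The inflation belongs to the protocol's analysis only.

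**Worst-case and break-even analyses are already planned.** They would bound the bias, since worst case fails every subject with no recorded failure and no 12-month test. Two limits remain. The SAP does not say that these analyses are run on ITT. Worst case also fails subjects with a clean test at or after Visit 10 who lack only the 12-month one, so it does not replace a correct ITT rule.

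**Missing the endocardial stage need not mean having no usable test.** Protocol 9.2.1 promises an attempt at 12-month status, timed from surgery, for subjects who refuse or cannot have the catheter procedure, and conversions to sternotomy or thoracotomy are followed for 12 months. That stands and may shrink the group. However, Protocol 4.4 lets those who withdraw before the second stage exit after the 1-month visit, and 9.2.1 sends unascertained cases back to the same missing-value rules.

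**The scenarios are soft.** The feasibility study staged the procedures 1 to 10 days apart, against 91 to 121 days here, and the protocol does not say that the one subject left follow-up. The 52% row is an extreme upper bound, not an expectation. Fixing all leavers as successes ignores items 5 to 7.

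**Conclusion.** The concern holds on the literal text, for ITT subjects who die or exit before Visit 10 with none of failure items 5 to 7 recorded: LOCF equals best case for them.

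Under the SAP the consequence is an upward bias in a supportive analysis. At a 70% rate among the rest, that is 71.2% against 67.1% with 9 early leavers, and 73.0% against 63.0% with 22, compared with counting them as failures.

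Under Protocol 9.7.1 and 9.9 the consequence is type I error above 2.5%: 2.8%, 6.2% and 20.5% with 2, 9 and 22 early leavers.

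These figures assume N=220, a 60% or 70% rate among the remaining subjects, and early-leaver counts that the documents do not give. The protocol's ITT counts all enrolled eligible subjects, and enrollment is at consent, so its N could differ from 220.

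**What to change.** 1. In SAP 5.3 and Protocol 9.9, state that LOCF may carry forward only the effectiveness status from a rhythm test done at or after Visit 10, or at or after the equivalent 6-month point from surgery for subjects assessed under Protocol 9.2.1.
2. In the same places, state that an ITT subject with no such test, including one who died, counts as a failure in the ITT analysis.
3. State that the worst-case and break-even analyses are run on ITT.
4. Reconcile Protocol 4.4 (exit after the 1-month visit) with 9.2.1 (attempted 12-month follow-up), because together they determine how many subjects fall into this gap.

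The cost is a few sentences and a less favourable ITT rate. The scoring changes need no new data. They should be made before the data are analyzed, so that the choice between readings is not driven by the results.

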5.4 Subject Disposition

The number of subjects in each analysis population will be presented along with reason for any exclusions. Subject accountability will be summarized by visit. The number of subjects who are enrolled, eligible for follow-up, and number completing clinical follow-up will be summarized for each protocol-required visit. In addition, the number of subjects who complete the study or exit early will be summarized by reason.

5.5 Demographics and Baseline Characteristics

Descriptive statistics will be presented for all clinically relevant baseline demographic, medical history, and clinical characteristic variables.

5.6 Analysis of Study Endpoints

The study will be considered successful if both the primary effectiveness and primary safety endpoints are statistically significant at the 0.025 level (one-sided).

Statistical Analysis Plan		Page 13 of 22
Sponsor	Study	Version
AtriCure	DEEP Pivotal Study	Version 2.0

5.6.1 Primary Effectiveness Endpoint

The primary effectiveness endpoint is freedom from any documented AF, atrial flutter, or atrial tachycardia lasting >30 seconds in duration through the 12-month follow-up visit in the absence of Class I or III AADs (with the exception of previously failed AADs at doses not exceeding those previously failed). Effectiveness failure events are described in detail in section 2.1.1.

5.6.1.1 Primary Analysis

The statistical analysis of the primary effectiveness endpoint will consist of a comparison of the proportion of patients who remain a primary effectiveness success at the 12-month visit to a historical control rate that is based on results from the feasibility trials and published literature. The primary effectiveness endpoint will be assessed with the following hypothesis:

$$H_0: p_E \leq 0.60$$

$$H_a: p_E > 0.60$$

where p_E = the proportion of primary effectiveness success. The hypothesis will be evaluated using a one-sided chi-squared test at a one-sided $\alpha=0.025$ level of significance. The objective will be met if the estimated one-sided p-value is < 0.025. The mITT population will be the primary population for this analysis. Missing values will be treated as described in the Missing Values section 5.3 with the primary method being the LOCF method.

The proportion of primary effectiveness successes will be calculated with subjects as the experimental unit (i.e., the subject will be considered a success if no primary effectiveness failure was recorded from the 6-month visit through the 12-month visit). The numerator of the proportion will be the number of subjects who are a primary effectiveness success, and the denominator will be the total number of subjects. The endpoint will be presented with the numerator and denominator, the proportion and its 95% two-sided exact binomial confidence interval, and the one-sided p-value.

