9.7.1 Primary Analyses

Primary Safety

The statistical analysis of the primary safety endpoint will consist of a comparison of the proportion of patients who fail to complete the trial without a primary safety endpoint event to a historical control rate that is based on results from the feasibility trials. Adverse events will be adjudicated in accordance with section 12.1. The proportion of primary safety failures will be calculated with subjects as the experimental unit (i.e., the subject will be considered a failure if a primary safety event was experienced within the timeframes defined in the endpoint). The numerator of the proportion will be the number of subjects who have a primary safety event, and the denominator will be the total number of subjects.

A normal approximation to the binomial distribution, Z-test will be conducted at a one-sided $\alpha=0.025$ level of significance to test the following hypothesis that the proportion of failures is significantly lower than the OPC:

$$H_o : p_s \geq 0.28 \quad vs. \quad H_a : p_s < 0.28$$

where p_s = the proportion of primary safety failures in the safety population. The safety population will be the primary population for this analysis. Missing values will be treated as described in the Missing Values section below.

Primary Effectiveness

The statistical analysis of the primary effectiveness endpoint will consist of a comparison of the proportion of patients who remain a primary effectiveness success at the 12-month visit to a historical control rate that is based on results from the feasibility trials and published literature. The proportion of primary effectiveness successes will be calculated with subjects as the experimental unit (i.e., the subject will be considered a success if no primary effectiveness failure was recorded from the 6-month visit through the 12-month visit). The numerator of the proportion will be the number of subjects who are a primary effectiveness success, and the denominator will be the total number of subjects.

An exact, one-sample binomial test will be conducted at a one-sided $\alpha=0.025$ level of significance to test the following hypothesis that the proportion of effectiveness successes is significantly higher than the OPC:

$$H_o : p_E \leq .60 \quad vs. \quad H_a : p_E > .60$$

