Statistical Analysis Plan		Page 5 of 22
Sponsor	Study	Version
AtriCure	DEEP Pivotal Study	Version 2.0

1 Introduction

This statistical analysis plan (SAP) describes the planned statistical methods to be used during the reporting and analysis of data collected under the Clinical Study Protocol CP2014-1 DEEP Pivotal Study. This SAP should be read in conjunction with the study clinical study plan (CSP) and case report forms (CRFs). This version of the SAP has been developed with respect to the Clinical Study Protocol CP2014-1 DEEP Pivotal Study Revision H 28Sep2022. Any revisions to the protocol or CRFs that impact the planned analyses may require updates to the SAP.

2 Study Objectives

The primary objective of this study is to evaluate the safety and effectiveness of a dual epicardial and endocardial ablation procedure for patients presenting with Persistent Atrial Fibrillation or Longstanding Persistent Atrial Fibrillation utilizing the AtriCure Bipolar System and AtriClip PRO LAA Exclusion System in an endoscopic or open ablation procedure, followed by an endocardial mapping and ablation procedure utilizing commercially available RF based, ablation catheters.

The effectiveness of the device will be demonstrated by establishing that the device effectively eliminates persistent and long-standing persistent atrial fibrillation, atrial flutter, or atrial tachycardia in a clinically significant proportion of treated patients.

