5.10 Protocol Deviations

Deviations from the procedures outlined in the CSP will be reported by investigational sites on the CRF. Protocol deviations will be summarized for all deviations and by type (i.e. deviation code) with total deviation counts and number of subjects with at least one deviation. A listing of all protocol deviations will be provided that includes details of each deviation (e.g. deviation reason, justification/corrective action, etc).

6 Changes from Planned Analyses

Any changes to planned statistical analyses determined necessary prior to performing the analyses will be documented in an amended Statistical Analysis Plan and approved prior to the analysis when possible. Any other deviations or changes from the planned analyses deemed necessary due to violation of critical underlying statistical assumptions, data characteristics, or missing data will be clearly described in the clinical study report with justification and rationale.

7 Subject Listings

Subject listings will be provided for the primary and secondary endpoints.

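### The SAP tests primary effectiveness with a one-sided chi-squared test where the protocol specifies an exact binomial test; without a continuity correction it can pass on one fewer success, with type I error above 0.025 at some sample sizes

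*SAP*

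**What the plan says.** Protocol 9.7.1, for primary effectiveness with a null success rate of 60% or less: "An exact, one-sample binomial test will be conducted at a one-sided" 0.025 level.

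SAP 5.6.1.1, same hypothesis and same level: "The hypothesis will be evaluated using a one-sided chi-squared test". The decision rule follows: "The objective will be met if the estimated one-sided p-value is < 0.025". The result is to be shown with "the proportion and its 95% two-sided exact binomial confidence interval, and the one-sided p-value".

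For the LAA exclusion endpoint, SAP 5.6.3.1 keeps the exact binomial test.

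The SAP says it was written against "Clinical Study Protocol CP2014-1 DEEP Pivotal Study Revision H 28Sep2022". The protocol available here is Rev H dated 11May2021. SAP section 6 provides for changes: "Any changes to planned statistical analyses determined necessary prior to performing the analyses will be documented in an amended Statistical Analysis Plan".

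**The concern.** The two documents name different tests for one of the two conditions that define study success, and the SAP does not mention the difference. A change made through the SAP is not irregular in itself. But this one is unexplained, and it leaves open whether a continuity correction is used.

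Because the p-value alone decides, the choice of test sets the number of successes needed. If the two tests have different pass marks at the final sample size, the trial could be positive under the SAP and negative under the protocol. The exact interval printed beside the p-value would then include 60%, and the true type I error would be above the stated 0.025. The primary population is the mITT set, whose size depends on follow-up, so nobody can say in advance that the final n will avoid such a size.

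**Working it through.** **Inputs.** Null rate 0.60, expected rate 0.70, 80% power, N=182 and "a one-sided alpha=0.025 level of significance" (protocol 9.3). Up to 220 treated, with about 20% attrition allowed (protocol 9.3). Success if one-sided p < 0.025 (SAP 5.6.1.1).

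**1. The plan's own figure.** Protocol 9.3 states: "normal approximation to the binomial distribution with continuity correction, a sample size of N=182 is required". The usual one-sample formula without correction gives

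n0 = [(1.960·√(0.6·0.4) + 0.842·√(0.7·0.3)) / 0.10]² = 181.1, rounded up to 182.

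With the correction, n = (n0/4)·[1 + √(1 + 2/(n0·0.10))]² = 191.0. So 182 is the uncorrected figure although the text names a correction. Protocol 9.3 therefore cannot be used to infer which form of chi-squared test the SAP intends.

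**2. Pass marks.** The final n is not given. I assume 176 to 220, where 176 = 220 × 0.80. For each n, find the smallest passing count r under three tests:

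- exact: P(X ≥ r | n, 0.60) < 0.025;
- uncorrected chi-squared: z = (r − 0.6n)/√(0.24n), upper-tail p < 0.025;
- corrected chi-squared: the same with r − 0.6n − 0.5 in the numerator.

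Type I error is the exact binomial probability of r or more successes at a true rate of 0.60; power is the same at 0.70.

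| n | Pass mark: exact / uncorrected / corrected | Type I error: exact / uncorrected | Power at 70%: exact / uncorrected |
|---|---|---|---|
| 176 | 119 / 119 / 119 | 2.26% / 2.26% | 78.2% / 78.2% |
| 180 | 122 / 121 / 122 | 1.90% / 2.76% | 76.9% / 81.5% |
| 182 | 123 / 123 / 123 | 2.11% / 2.11% | 78.7% / 78.7% |
| 192 | 129 / 129 / 130 | 2.41% / 2.41% | 82.4% / 82.4% |
| 205 | 138 / 137 / 138 | 1.85% / 2.62% | 82.0% / 85.7% |
| 210 | 141 / 140 / 141 | 1.97% / 2.77% | 83.6% / 87.0% |
| 220 | 147 / 147 / 147 | 2.21% / 2.21% | 86.5% / 86.5% |

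**3. Over all 45 sizes.**

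- The uncorrected test needs exactly one fewer success at 16 sizes: 177, 180, 183, 186, 188, 191, 194, 197, 199, 202, 205, 208, 210, 213, 216 and 218. Its type I error exceeds 0.025 at those same 16, ranging from 2.53% to 2.85%.
- Mean type I error is 2.42% uncorrected and 2.13% exact. The exact test never exceeds 2.498%.
- The corrected test needs one more success than the exact test at 7 sizes (178, 181, 189, 192, 200, 211, 219) and never exceeds 0.025. At a true 70% it disagrees with the exact test 0.6% of the time on average.
- The exact test and the exact lower limit gave the same decision at every count and every n.
- Widening the range to 150–220 gives 26 discordant sizes of 71, with a maximum type I error of 2.86%.

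**4. Two boundary cases.** At 140/210, z = (140 − 126)/√50.4 = 1.972, so p = 0.0243 and the SAP test passes. The exact p is 0.0277 and the exact lower limit is 59.85%. At 129/192 the corrected z = (129 − 115.2 − 0.5)/√46.08 = 1.959, so p = 0.02504 and it fails, while the exact p is 0.0241 and passes.

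**5. How often the uncorrected and exact tests disagree.**

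| True rate | At the 16 sizes | Mean over 45 sizes |
|---|---|---|
| 60% | 0.7% to 0.9% | 0.3% |
| 66% | – | 2.1% |
| 70% | 3.1% to 4.6% | 1.4% |

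**The case against.** Several points can be made for the SAP.

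- The inflation needs an uncorrected test, and the SAP does not say which form it means; a corrected test would be conservative. This stands as a condition on the result. It also shows that the pass mark depends on a choice the SAP leaves unstated.
- The effect is small: at most one success, mean type I error below 0.025, and no difference at 182 or 220. The count of 16 in 45 describes an assumed range and is not a probability that the trial lands there. All of this stands and limits the weight of the point.
- The primary safety endpoint uses a normal-approximation Z-test, so approximate tests are accepted in this trial. But that test is the same in protocol 9.7.1 and SAP 5.6.2.1. It is no precedent for changing the effectiveness test between documents.
- The exact interval follows a general default in SAP 5.1.1 and does not decide success. True, but a primary table whose interval includes the performance criterion while its p-value claims success would still need explaining.
- The 28Sep2022 protocol version may have made the same change. This cannot be checked here, and the fix allows for it. Even so, the missing correction rule and the possible clash with the interval remain on the SAP text alone.
- Restoring the exact test gives up some power against the uncorrected test. That is so; the cost is stated under the fix.

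**Conclusion.** The concern holds. The SAP and the 11May2021 protocol specify different tests for the primary effectiveness decision, and the SAP explains neither the change nor the continuity correction. The consequence is limited to one boundary count at certain sample sizes. There, the uncorrected test would declare success where the exact test does not, with type I error up to 2.85% for n between 176 and 220. This rests on the uncorrected reading and on that assumed range for the mITT n. It should be corrected before analysis because it governs the pass mark of a pivotal single-arm trial, although the chance that it changes the outcome is small.

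**What to change.** In SAP 5.6.1.1, replace the chi-squared test with the exact one-sample binomial test at one-sided 0.025, as SAP 5.6.3.1 already does for LAA exclusion. This holds type I error at or below 0.025 and always agrees with the exact interval. If the 28Sep2022 protocol version did change the test, cite it in the SAP and give the reason and the continuity-correction rule.

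The cost is one sentence and one line of code. No power is lost against the test in the 11May2021 protocol. Against the uncorrected chi-squared test, one more success is needed at the 16 discordant sizes. At a true 70% that costs 3.1 to 4.6 points of power there (87.0% to 83.6% at n=210) and 1.4 points averaged over the 45 sizes.
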